## 1. OBJECTIVES

### 1.1. Primary Objective

- To determine the therapeutic efficacy (as measured by response rate) of abatacept + ixazomib + dexamethasone in multiple myeloma patients who have relapsed (or who are primary refractory) following treatment with their first proteasome inhibitor-containing regimen (excluding ixazomib), compared to historical controls of ixazomib + dexamethasone.

### 1.2. Secondary Objectives

- To assess the toxicity profile of abatacept + ixazomib + dexamethasone in multiple myeloma patients who have relapsed (or who are primary refractory) following treatment with their first proteasome inhibitor-containing regimen (excluding ixazomib), compared to historical controls of ixazomib + dexamethasone.
- To assess progression-free and overall survival profile of abatacept + ixazomib + dexamethasone in multiple myeloma patients who have relapsed (or who are primary refractory) following treatment with their first proteasome inhibitor-containing regimen (excluding ixazomib), compared to historical controls of ixazomib + dexamethasone.

#### Exploratory Objective

- Assess whether myeloma expression of CD28, CD86, serum kynurenine, and/or IL-6 are correlated with specific clinical outcomes.

## 2. BACKGROUND

### 2.1. Multiple myeloma and the pro-survival/chemotherapy-resistance effect of CD28 activation

Multiple myeloma (MM) is a malignancy of post-germinal center, Ig class-switched BM-resident plasma cells (PC) that comprises 20% of all hematologic malignancies (second only to non-Hodgkin's lymphoma) and is incurable for most patients. Myeloma cells are highly dependent on interactions with BM stromal niches for their survival (1), and MM is rarely found outside of the BM until very late in the disease course. Furthermore, the anti-myeloma efficacy of the newer chemotherapy agents is thought to be due in part to their disruption of MM-bone marrow stromal cell (BMSC) interactions via unclear mechanisms (2), although immune modulation has been clearly implicated. In defining which specific receptors interact with the stromal niche, we found that CD28 expressed on myeloma cells (which correlates significantly with poor prognosis and disease progression(3-6) transduces a survival signal that confers significant protection against chemotherapy, growth factor deprivation and other stresses (7-9). We have subsequently found that PC-intrinsic CD28 function is also essential for the survival of normal BM-resident long lived plasma cells (LLPC) and maintenance of durable antibody responses (10). Thus it appears CD28 regulates fundamental aspects of normal PC biology that are conserved in MM biology due to their essential role in survival(1).

[figure not shown]
The discovery that CD28 plays a key pro-survival role in MM/PC points to BMSC expressing the CD28 ligands CD80 and/or CD86 as the cellular partners in the myeloma niche. CD80/CD86+ cells are predominantly immune cells, including B cells and myeloid cells (eosinophils (11),

basophils (12), monocyte/macrophages, and most highly expressed on myeloid DC). DC have been best characterized as professional antigen presenting cells involved in T cell activation (13), but also support normal B $\rightarrow$ PC differentiation via cell-cell contact and production of the Pro-survival cytokines (14-16),(17). Consistent with this role in normal PC biology, we and others have found that myeloid DC (both mature and immature), plasmacytoid DC and monocyte/macrophages are preferentially recruited into murine myeloma tumors as well as the myelomatous regions in patient BM, and *in vitro* can by themselves (i.e. without other BMSC) directly support the survival of MM cells in a cell-contact dependent manner (18-24). Thus the myeloma ME represents a clear case where normal immune cells are functioning as bona fide pro-survival stroma(25). Interestingly, some of the most effective therapies for MM have myelotoxicity as the major side effect.

We have also found that CD28 on MM cells directly modulates the stromal myeloid DC via ligation of CD80/CD86, inducing DC production of IL-6 and the immunosuppressive enzyme indoleamine 2, 3 dioxygenase (IDO) (10, 26). IL-6 is a well-established B-lineage survival cytokine. IDO catabolizes the essential amino acid tryptophan (Trp) into the toxic metabolite kynurenone, depleting Trp from the microenvironment and resulting in effector T cell suppression (27) and regulatory T cell (Treg) generation (28). We have recently defined the CD80/CD86 signal transduction pathways in human DC, finding that both IL-6 and IDO production require activation of a downstream PI3K $\rightarrow$ Akt $\rightarrow$ NF- $\kappa$ B pathway that modulates FoxO3a transcriptional activity - and this pathway involves previously unrecognized crosstalk with Notch1 signaling(29). Thus in addition to directly transducing a pro-survival signal to the MM cell, CD28 back-signaling through DC CD80/CD86 creates a stromally-produced soluble microenvironment that supports MM survival and suppresses anti-tumor immunity (26). This is, however, not unique to transformed MM cells, as we have found that normal PC also interact with DC within the BM niche, and this PC-DC interaction also results in both a CD28/CD80-CD86 dependent survival signal to the PC and induction of IL-6/IDO production from the DC ((30) and unpublished data).

[figure not shown]

Although MM is initially responsive to chemotherapy, it almost invariably relapses with progressively more chemo-resistant disease, and it is this resistant disease that is the primary cause of patient deaths. Our data suggests that CD28 expressed on myeloma cells interacts with CD80/CD86 on stromal DC in the ME or CD86 on the MM cells themselves, and this transduces a major pro-survival signal to the MM cells that is significant component of the chemotherapy resistance in relapsed disease. Our preclinical murine model and single patient results suggest that blocking the MM CD28 – DC CD80/CD86 interaction with abatacept can re-sensitize MM cells to chemotherapy, which would have major clinical impact.

The first-generation proteasome inhibitor (PI) bortezomib is the backbone of chemotherapy treatment of newly diagnosed MM patients, and resistance to BZ is a primary cause of disease relapse. We propose to examine the ability of abatacept to reverse this resistance in a Phase II clinical trial in relapsed MM patients that have progressed after being treated with a proteasome inhibitor -containing regimen (bortezomib, carfilzomib, but not ixazomib), as these patients are likely to have disease that is relatively resistant to the FDA-approved 2nd generation proteasome inhibitor ixazomib. While one standard of care regimen for bortezomib-resistant patients is ixazomib (ixa) + dexamethasone (dex, 40 mg weekly), because of the pre-existing resistance to

proteasome inhibition this regimen has only modest clinical efficacy (31% overall response rate (34)). We believe that concurrent treatment with abatacept + ixazomib + dexamethasone will overcome this proteasome inhibitor-resistance, resulting in a significantly higher overall response rate.

## **2.2. Study Drugs**

All the study drugs used in the protocol are FDA-approved for the treatment of either multiple myeloma (i.e., ixazomib and dexamethasone) or, rheumatoid arthritis (i.e., abatacept). A detailed discussion of the preclinical pharmacology, pharmacokinetics, and toxicology of each study drug can be found in the Package Inserts (see **Appendix F**).

### **2.2.1. Abatacept**

Abatacept (ORENCIA®) is a soluble fusion protein that consists of the extracellular domain of human cytotoxic T-lymphocyte-associated antigen 4 (CTLA-4) linked to the modified Fc (hinge, CH2, and CH3 domains) portion of human immunoglobulin G1 (IgG1). Abatacept is produced by recombinant DNA technology in a mammalian cell expression system.

Abatacept, a selective costimulation modulator, inhibits T cell (T lymphocyte) activation by binding to CD80 and CD86, thereby blocking interaction with CD28. This interaction provides a costimulatory signal necessary for full activation of T lymphocytes implicated in the pathogenesis of RA.

### **2.2.2. Ixazomib**

Ixazomib (NINLARO®) is a reversible proteasome inhibitor and antineoplastic agent. Ixazomib preferentially binds and inhibits the chymotrypsin-like activity of the beta 5 subunit of the 20S proteasome.

Ixazomib citrate, a prodrug, rapidly hydrolyzes under physiological conditions to its biologically active form, ixazomib. *In vitro*, ixazomib induced apoptosis against myeloma cells from patients who had relapsed after multiple prior therapies, including bortezomib, lenalidomide, and dexamethasone.

The NCCN Guidelines Version 3.2017 for Multiple Myeloma ([https://www.nccn.org/professionals/physician\\_gls/PDF/myeloma.pdf](https://www.nccn.org/professionals/physician_gls/PDF/myeloma.pdf)) has included the combination of ixazomib plus dexamethasone as a treatment option for patients with relapsed/refractory multiple myeloma who have received at least one prior therapy.

### **2.2.3. Dexamethasone**

Dexamethasone is a synthetic adrenal corticosteroid with potent anti-inflammatory properties. In addition to binding to specific nuclear steroid receptors, dexamethasone also interferes with NF- $\kappa$ B activation and apoptotic pathways. Dexamethasone's anti-myeloma effect is thought to occur via binding to the corticosteroid receptor, which induces apoptosis in B lineage lymphocytes that include plasma cells.

## **2.3. Rationale**

The rationale for the combination of abatacept + ixazomib + dexamethasone is detailed Section 2.1 above. The overall hypothesis of this proposal is that blocking the pro-survival CD28 activation on myeloma cells with abatacept will reverse chemotherapy resistance and re-sensitize multiple

Roswell Park Protocol No.: I 47217

myeloma cells to agents they were previously resistant to. We will specifically test this hypothesis in multiple myeloma patients who have relapsed following treatment with a bortezomib-containing regimen, with the trial hypothesis being that abatacept co-treatment will reverse pre-existing resistance to proteasome inhibitors and significantly improve response rates to the second-generation proteasome inhibitor, ixazomib.

### **3. INCLUSION AND EXCLUSION CRITERIA**

#### **3.1. Inclusion Criteria**

To be included in this study, participants must meet the following criteria:

1. Patients with multiple myeloma who have relapsed (or who are primary refractory) following treatment with a proteasome inhibitor-containing regimen (excluding ixazomib), and who have not been treated with a second proteasome inhibitor (ixazomib, bortezomib, carfilzomib, or other proteasome inhibitor).
2. Age  $\geq$  18 years of age at time of consent.
3. Have an ECOG Performance Status of  $\leq$  2 at study entry. Refer to **Appendix A**.
4. Must be free of systemic infection:
  - Subjects with active infections (whether or not they require antibiotic therapy) may be eligible after complete resolution of the infection.
  - Subjects on antibiotic therapy must be off antibiotics for at least 7 days before beginning treatment.
5. Have the following clinical laboratory values:
  - Absolute neutrophil count  $\geq$  750/mm^3
  - Platelet count  $\geq$  25,000/mm^3
  - Creatinine clearance  $\geq$  30 mL/min
  - Total bilirubin: AST (SGOT) and ALT (SGPT)  $\leq$  3x ULN
6. Patient's multiple myeloma cells are positive for CD28 or CD86 expression by flow cytometry or immunohistochemistry (in any proportion). CD28 or CD86 positivity can have been determined on previous bone marrow aspirates or biopsies.
7. Disease free of prior malignancies for  $>2$  years with exception of currently treated basal cell, squamous cell carcinoma of the skin, or carcinoma "in situ" of the cervix or breast.
8. Participants of child-bearing potential must agree to use adequate contraceptive methods (e.g., hormonal or barrier method of birth control; abstinence) prior to study entry. Should a woman become pregnant or suspect she is pregnant while she or her partner is participating in this study, she should inform her treating physician immediately.
9. Participant must understand the investigational nature of this study and sign an Independent Ethics Committee/Institutional Review Board approved written informed consent form prior to receiving any study related procedure.

Refer to **Appendix B** for the ELIGIBILITY VERIFICATION FORM: INCLUSION CRITERIA CHECKLIST.

Roswell Park Protocol No.: I 47217

### **3.2. Exclusion Criteria**

Participants will be excluded from this study for the following:

1. Prior treatment with ixazomib.
2. Inability to take ixazomib or abatacept.
3. Life expectancy less than 4 months.
4. Patients with a known diagnosis of plasma cell leukemia.
5. Known active tuberculosis or fungal infection.
6. Known seropositive for or active viral infection with, human immunodeficiency virus (HIV), hepatitis B virus (HBV), or hepatitis C virus (HCV). Patients who are seropositive because of immunization with the hepatitis B virus vaccine are eligible.
7. Uncontrolled intercurrent illness including, but not limited to, ongoing or active infection, symptomatic congestive heart failure, unstable angina pectoris, cardiac arrhythmia, or psychiatric illness/social situations that would limit compliance with study requirements.
8. Any condition, including the presence of laboratory abnormalities, which places the subject at unacceptable risk if he/she were to participate in the study or, which confounds the ability to interpret data from the study.
9. Pregnant or nursing female participants.
10. Unwilling or unable to follow protocol requirements.
11. Any condition which in the Investigator's opinion deems the participant an unsuitable candidate to receive study drug.
12. Received an investigational agent within 30 days prior to enrollment.

Refer to **Appendix C** for the ELIGIBILITY VERIFICATION FORM: EXCLUSION CRITERIA CHECKLIST.

### **3.3. Special Populations**

The following Special Populations will be excluded:

1. Cognitively impaired adults/adults with impaired decision-making capacity, as there are other standard of care therapies available for these myeloma patients that are known to be effective,
2. Individuals who are not yet adults, as multiple myeloma is extremely uncommon in this population and,
3. Pregnant women, as the effects of the combination of abatacept and ixazomib on the fetus are not known.

Prisoners are not excluded from this trial if they otherwise qualify and wish to voluntarily participate. If a prisoner is enrolled or a patient becomes incarcerated while participating in the study, the Roswell Park IRB will be contacted to allow for review of the study using the prisoner criteria [(refer to: CHECKLIST: Prisoners (HRP-415)].

### **3.4. Inclusion of Women and Minorities**

Both men and women and members of all races and ethnic groups are eligible for this study.

Roswell Park Protocol No.: I 47217

#### **4. LOCAL AND STUDY-WIDE NUMBER OF SUBJECTS**

A maximum of 19 patients at multiple sites, including Roswell Park will be enrolled. Accrual is expected to take up to 4 years.

Patients will participate in this study for approximately 48 months from the time of enrollment.

#### **5. LOCAL AND STUDY-WIDE RECRUITMENT METHODS**

Participants will be identified/recruited/screened from patients at the Lymphoma/Myeloma Clinic at Roswell Park and from other participating sites.

#### **6. MULTI-SITE RESEARCH**

It is the responsibility of the Principal Investigator to ensure that:

- All sites have the most current version of the protocol, consent document, and HIPAA authorization.
- All required approvals (initial, continuing review and modifications) have been obtained at each site (including approval by the site's IRB of record).
- All modifications have been communicated to sites, and approved (including approval by the site's IRB of record) before the modification is implemented.
- All engaged participating sites will safeguard data, including secure transmission of data, as required by local information security policies.
- All local site investigators will conduct the study in accordance with applicable federal regulations and local laws.

All non-compliance with the study protocol or applicable requirements will be reported in accordance with local policy.

Refer to **Appendix G: Instructions for Network Sites.**

#### **7. STUDY TIMELINES**

A maximum of 19 participants at multiple sites, including Roswell Park will be enrolled. Accrual is expected to take 4 years, with safety follow-up at 30 days from the end of investigational treatment. Additional follow-up safety evaluations will occur monthly through 48 months.

#### **8. STUDY ENDPOINTS**

##### **8.1. Primary Endpoints**

- Response rate will be used to determine the therapeutic efficacy of abatacept + ixazomib + dexamethasone in MM patients who have relapsed (or who are primary refractory) following treatment with their first proteasome inhibitor-containing regimen (excluding prior treatment with ixazomib), compared to historical controls of ixazomib + dexamethasone.

##### **8.2. Secondary Endpoints**

- The NCI Common Terminology Criteria for adverse events (CTCAEv5.0) will be used to evaluate toxicity.

- Progression-free survival is defined as the time from the date of the first study treatment to the date of first observed disease progression or death due to any cause. Study participants will be followed every 3 months following end of treatment (until initiation of a new therapy or until death, whichever occurs first) to determine overall survival.

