### **11.7. Post-Treatment Follow-Up Evaluations**

Follow-up safety evaluations will occur 30 days ( $\pm$  3 days) after last dose of study drug or until resolution of any drug-related toxicity (telephone contact is acceptable).

- Complete history and physical examination (with vital signs and weight)
- Hematology: CBC with differential.
- Chemistry: CMP to include chloride, CO2, potassium, sodium, BUN, glucose, calcium, creatinine, total protein, albumin, total bilirubin, alkaline phosphatase, AST, ALT, A/G ratio, BUN/creatinine ratio, osmol (Calc), anion gap). In addition: phosphorus, magnesium, lactate dehydrogenase (LDH).
- ECOG Performance Status (**Appendix A**).
- Blood draw for serum kynurenine and IL-6 levels.
- Concomitant medication: List any ongoing medications with dose changes, as applicable.
- Adverse events.

The following assessments are only **required for patients that achieve a Stringent CR**:

- Disease Status Evaluation:
  - Blood:
    - Qualitative immunoglobulins:
    - SPEP
    - Serum IFE
    - Serum free light chain
  - Urine:
    - 24-hour UPEP and UIFE

Additional follow-up safety evaluations will occur monthly through 48 months. All patients with abatacept-related toxicity will be followed until it resolves to  $\leq$  Grade 1. After 48 months, patients will move to long-term follow-up and will be monitored for survival status (telephone contact or medical record check is acceptable). Patients will be monitored until death or study closure, whichever occurs first.

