#### **11.7.1. Survival Status**

Patients that discontinue treatment due to progressive disease, toxicity (treatment-related or unrelated) or withdrawal for any other reason will be monitored every 3 months after end of treatment for one year, then annually until death or study closure, whichever occurs first (telephone contact or medical record check is acceptable) to document survival status.

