### **11.8. Long Term Follow-Up Evaluations**

Disease-free survival status assessments for patients that achieve a Stringent CR will be performed every 3 months ( $\pm$  7 days) after the completion of treatment until disease progression or death due to any cause; whichever comes first.

Roswell Park Protocol No.: I 47217

- Disease Status Evaluation:
  - Blood:
    - Qualitative immunoglobulins:
    - SPEP
    - Serum IFE
    - Serum free light chain
  - Urine:
    - 24-hour UPEP and UIFE

Participants who are unavailable for follow-up evaluations should be classified as lost to follow-up for 1 of the following reasons:

- Lost to follow-up: For a participant to be considered lost to follow-up, the investigator must make two separate attempts to re-establish contact with the participant. The attempts to re-establish participant contact must be documented (e.g., certified letter).
- Death: Date and cause of death will be recorded for those participants who die within 30 days after last dose of study drug (telephone verification is acceptable).

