### **19.5. Secondary Analyses**

The secondary objectives include: 1) assessment of the abatacept + ixazomib + dexamethasone toxicity profile; 2) assessment of progression-free and overall survival.

The adverse events and drug related toxicities will be summarized by grade using frequencies and relative frequencies. The rate of grade 3 or higher toxicities that are probably or definitely related to abatacept will be reported with 90% confidence intervals obtained using Jeffrey's prior method.

Progression-free and overall survival will be summarized using standard Kaplan-Meier methods; where estimates of median survival and survival rates will be obtained with 90% confidence intervals

**Safety Analysis:** The NCI Common Terminology Criteria for adverse events (CTCAEv5.0) will be used to evaluate toxicity. We will consider a toxicity to be an adverse event that is possibly, probably or definitely related to treatment. The maximum grade of toxicity for each category of interest will be recorded for each patient and the summary results will be tabulated by category and grade. Regimen limiting toxicities (RLT) include any Grade 3 or greater toxicity probably or definitely related to abatacept. The rate of grade 3 or higher toxicities that are probably or definitely related to abatacept will be reported with 90% confidence intervals obtained using Jeffrey's prior method.

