Acyclovir 		X				Daily with start of ixazomib and continue for 1 month following discontinuation of ixazomib						
Concomitant Medications 	X	X 				X				X	X	
Adverse Events		X	X	X	X	X	X	X	X	X	X	
Survival Status 											X	X

1 Performed within 28 days prior to first dose of study drug (unless otherwise noted).  
 2 Follow-up safety evaluations will occur 30 days ( $\pm$  3 days) after last dose of study drug or until resolution of any drug-related toxicity. Additional follow-up safety evaluations will occur monthly through 48 months. All patients with abatacept-related toxicity will be followed until it resolves to  $\leq$  Grade 1. After 48 months, patients will move to long-term follow-up and will be monitored for survival status for up to an additional 3 years (telephone contact or medical record check is acceptable) to document survival status. Patients will be monitored until initiation of a new therapy or until death, whichever occurs first.  
 3 Disease free survival for patients that achieve a Stringent CR: disease status evaluation with blood (QIgs, SPEP, serum IFE, serum free light chains), urine (24 hour UPEP) will be performed every 3 months ( $\pm$  7 days) after the completion of treatment until disease progression or death due to any cause; whichever comes first.  
 4 Vital signs (temperature, heart rate, respiratory rate, blood pressure), body weight and, height. Height collected at baseline only.  
 5 Skeletal survey, bone marrow MRI or PET/CT for quantification of bone lesions, done at baseline (within 8 weeks of first dose) and then annually or as per local institutional guidelines.  
 6 Bone marrow biopsy and aspiration will be used for assessment of CD28 and CD86 expression on MM cells. A fresh sample is not required if CD28 or CD86 positivity has been determined on a previous bone marrow aspirate or biopsy. For patients that do undergo biopsy, an additional 10-20 mL of aspirate (heparinized or in green tops) will be collected for isolation of MM cells.  
 7 Hematology (i.e., CBC with differential). Note: Patients experiencing Grade 4 neutropenia should be monitored according to institutional guidelines. As needed at each study visit as determined by the Investigator or study physician.  

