 8 Chemistry: CMP to include chloride, CO2, potassium, sodium, BUN, glucose, calcium, creatinine, total protein, albumin, total bilirubin, alkaline phosphatase, AST, ALT, A/G ratio, BUN/creatinine ratio, osmol (Calc), anion gap). In addition: phosphorus, magnesium, lactate dehydrogenase (LDH).  
 9 At baseline, perform  $\leq$  7 days prior to start of study treatment.  
 10 Blood for serum kynurenine and IL-6 (Refer to Section 11.9.1).

Evaluation	Baseline 	Cycle 1				Cycle 2 and every cycle thereafter (± 7 days)				End of Treatment (CR, progression or, off study)	Post-Treatment Follow-Up 	Long Term Follow-Up 
		Day 1	Day 2	Day 8 & Day 15 (± 2 days)	Day 22 (± 2 days)	Day 1	Day 8 (± 2 days)	Day 15 (± 2 days)	Day 22 (± 2 days)			
11	Abatacept IV loading Day 1 Cycle 1: followed by 125 mg SQ on Day 2.											
12	SQ, 125 mg; continue 125 mg SQ, once weekly thereafter.											
13	Ixazomib 4 mg po on Days 1, 8, and 15 of a 28-day cycle.											
14	Dexamethasone 40 mg po of Days 1, 8, 15, and 22 of a 28-day cycle. Weekly dose of dexamethasone may be split into two doses at the discretion of the treating physician.											
15	Acyclovir 400 mg po BID with the start of ixazomib treatment for varicella prophylaxis and continue one month past the discontinuation of ixazomib treatment.											
16	Medications taken in the month prior to registration (ongoing or discontinued).											
17	Medications taken within 1 week prior to first dose of study drug.											
18	Patients that discontinue treatment due to progressive disease, toxicity (treatment-related or unrelated) or withdrawal for any other reason will be monitored every 3 months after end of treatment (telephone contact acceptable) to document survival status. Patients will be monitored until initiation of a new therapy or until death, whichever occurs first.											
19	Bone marrow biopsy/aspirate with flow cytometry for CD28 and CD86 upon progression, or to confirm Stringent CR or CR. For patients who are progressing, an additional 20 mL of aspirate (heparinized or in green tops) will be collected for isolation of MM cells (see Section 11.9.2 regarding sample handling).											

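### The protocol gives conflicting end points for survival follow-up, and overall survival has no stated time origin or censoring rule

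*Combined protocol and SAP*

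**What the plan says.** Section 1.2 makes OS part of a secondary objective: "To assess progression-free and overall survival profile of abatacept + ixazomib + dexamethasone in multiple myeloma patients", set against historical controls. The rules for following survival are spread over five places.

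- **Section 8.2:** contact every 3 months after end of treatment, "until initiation of a new therapy or until death, whichever occurs first) to determine overall survival".
- **Appendix E, footnote 18:** contact every 3 months for patients who stop treatment for progression, toxicity or any other reason. "Patients will be monitored until initiation of a new therapy or until death, whichever occurs first".
- **Section 11.7.1:** the same patients, every 3 months for one year and "then annually until death or study closure, whichever occurs first".
- **Section 11.7:** monthly safety evaluations through 48 months, then survival status. "Patients will be monitored until death or study closure, whichever occurs first".
- **Appendix E, footnote 2:** after month 48, patients "will be monitored for survival status for up to an additional 3 years". The footnote then ends with a stop at new therapy or death.

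On analysis, Section 19.5 says "Progression-free and overall survival will be summarized using standard Kaplan-Meier methods", with 90% confidence intervals. Section 8.2 gives progression-free survival a time origin (first study treatment) and an event. It gives OS neither in words.

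Section 11.8, in its list on participants unavailable for follow-up, adds: "Date and cause of death will be recorded for those participants who die within 30 days after last dose of study drug".

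**The concern.** A site cannot comply with both footnote 18 and Section 11.7.1, because they cover the same patients and end follow-up at different points. In a multi-site trial, some sites may work from the schedule in Appendix E and others from Section 11. One Kaplan-Meier curve would then mix patients followed to death with patients whose contact ended at new therapy.

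Section 8.2 sets how long patients are followed; it is not a censoring rule. But where contact ends at new therapy and no other rule applies, the last contact becomes the censoring date by default. Starting new therapy is usually linked to the course of the disease, so this censoring is likely informative. The curve is too high if the death hazard rises after new therapy. It is too low if the hazard falls afterwards, or if patients too ill for new therapy die sooner. Deaths that were never collected cannot be recovered by a later choice of analysis.

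**Working it through.** **1. The plan's own figures.** The documents give no figure for OS to reproduce. Their only power figure is for response (Sections 19.1 and 19.4): n = 19, at least 9 responses, 30% against 60%. The exact binomial gives power 0.912 (stated 90%) and type I error 0.084 (limit 0.1). It uses no survival data, so this point does not touch it.

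**2. The rules side by side.**

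| Place | Contact interval | Ends at |
|---|---|---|
| 8.2 | every 3 months | new therapy or death |
| App. E fn 18 | every 3 months | new therapy or death |
| 11.7.1 | every 3 months for 1 year, then annual | death or study closure |
| 11.7 | survival status after month 48, interval not given | death or study closure |
| App. E fn 2 | after month 48, interval not given | 3-year cap; also new therapy or death, scope unclear |

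So the end point, the contact interval after year 1 and the 3-year cap all conflict. Sections 11.7 and 11.7.1 share an end point but not a start: one takes up survival status after month 48, the other at end of treatment.

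**3. Illustration of size.** Every rate below is an assumption. The calculation is a worst case: all patients are followed under 8.2 alone, and no other contact reveals a death.

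Inputs:
- A share u = 0.7 of patients would start new therapy if alive, at a median of m = 8 months, so L = ln 2/8 = 0.0866 per month.
- Monthly death hazards before/after new therapy (h1/h2) are A 0.01/0.04, B 0.02/0.04, C 0.03/0.03, D 0.04/0.02. Patients who never start keep h1.
- The horizon is 48 months (Sections 4 and 7), and k = L + h1.

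Formulas:
- True survival: S(t) = u{e^(−kt) + L[e^(−h2·t) − e^(−kt)]/(k − h2)} + (1 − u)e^(−h1·t)
- Kaplan-Meier censored at new therapy estimates e^(−h1·t)
- Deaths seen by month 48: u(h1/k)(1 − e^(−48k)) + (1 − u)(1 − e^(−48·h1)), divided by 1 − S(48)

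Set A in full: k = 0.0966. Deaths seen = 0.7 × 0.1035 × 0.990 + 0.3 × 0.381 = 0.186. All deaths = 1 − S(48) = 0.661. Share seen = 0.186/0.661 = 28%. At 24 months, censored OS is e^(−0.24) = 0.787 and true OS is 0.610.

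| Set | Deaths seen of total (n = 19) | Share seen | 24-month OS, censored vs true | Error (points) |
|---|---|---|---|---|
| A | 3.5 of 12.6 | 28% | 0.787 vs 0.610 | +18 |
| B | 6.0 of 14.3 | 42% | 0.619 vs 0.518 | +10 |
| C | 7.8 of 14.5 | 54% | 0.487 vs 0.487 | 0 |
| D | 9.1 of 14.0 | 65% | 0.383 vs 0.473 | −9 |

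**4. Sensitivity.**
- *Time to new therapy.* With u = 0.7, the share seen across the four sets is 22–54% at a median of 4 months and 39–76% at 16 months.
- *Uptake.* With a median of 8 months, the share seen is 59–86% at u = 30% and 15–49% at u = 95%.
- *Frailer patients never treated again.* With hazard 0.06 in those who never start and 0.02 in the others throughout, 24-month OS is 41% censored against 50% true (u = 0.7, median 8 months).
- *Precision.* In set C, where there is no bias, the simulated 5th–95th percentile range of 24-month OS at n = 19 is 22–76% under 8.2 and 32–68% with full follow-up.

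**5. Cross-check with a different model.** This simulation assumes medians of 6 months to progression and 60 months to death without progression, with new therapy starting at progression.
- With 90% starting, and median survival 15 months afterwards (6 if untreated), median OS is 26.6 months censored against 20.3 true.
- With 70% starting, and 36 months afterwards (3 if untreated), it is 16.1 against 23.9.
- With 70% starting, and 15 months afterwards (6 if untreated), it is 18.9 against 18.3.

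Both directions occur here too, as does a case with almost no change.

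**The case against.** Four objections carry weight.

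**Later deaths may still be found.** A reader might infer that under 8.2 every death after new therapy is lost. The text does not support that. Sections 7 and 11.7 schedule monthly safety evaluations through 48 months with no stated stop at new therapy, and these could reveal deaths. But nothing says they continue after new therapy, and footnote 2, which repeats them, ends with a new-therapy stop of unclear scope. So later deaths may be missed, and the figures above are a worst case.

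**The event is clear enough.** A reader might say that OS has no event. Death is implied by the name and by the follow-up to death in 8.2. The gaps are the time origin and the censoring rule.

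**Section 11.8 is not an OS rule.** A reader might infer that only deaths within 30 days of the last dose are dated. That sentence is one item in a list on participants unavailable for follow-up, while 11.7 and 11.7.1 require monitoring until death. It is an ambiguity to clear up, not a limit on OS.

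**The consequence is limited.** OS is secondary and descriptive, with 19 patients. Section 1.2 names historical controls, but 19.5 gives no OS benchmark or test, and no stopping or go/no-go rule uses OS. The size and direction of the bias come wholly from assumed rates. All of this stands, and it limits the importance of the point. It does not remove the contradiction, which is in the text and depends on no assumption.

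**Conclusion.** The point holds as an internal contradiction together with an incomplete definition. Section 8.2 and footnote 18 end survival follow-up at new therapy; 11.7.1, for the patients of footnote 18, does not. The contact interval and the 3-year cap also conflict. No passage gives OS a time origin or a censoring rule.

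The documents show that bias is possible; they do not show its size or sign in this trial. A reader might infer that OS will be overstated, but sets C and D show no error or an error downward. Nor do the documents support a fixed uptake above which most deaths are missed, because that point moves with the assumed time to new therapy and hazards.

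It should be fixed because sites need one instruction and uncollected deaths cannot be restored later. It does not bear on the primary conclusion.

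**What to change.** - **Follow-up (8.2 and Appendix E footnotes 2 and 18):** use the 11.7.1 rule. Collect survival status from end of treatment, by telephone or chart check, regardless of new therapy, until death, withdrawal of consent, loss to follow-up or study closure.
- **Consistency:** state one contact interval, reconcile the 3-year cap in footnote 2, and align 11.7 with 11.7.1.
- **Deaths:** record the date of every death known during this follow-up, and make clear that the 30-day item in 11.8 does not limit this.
- **Definition (8.2 and 19.5):** define OS as the time from first study treatment, the origin already used for progression-free survival, to death from any cause. Censor at the date last known alive, not at new therapy.

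The cost is a wording change and a few more telephone or chart contacts in at most 19 patients, by means that 11.7 and 11.7.1 already allow. No visits or samples are added.
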